#### **7.1.11 30-Month Treatment Visit (Visit 10) and subsequent visits performed annually (Visit 12, Visit 14 etc)**

The following investigations will be performed:

- Physical examination including height, weight and pubertal status
- Vital signs (blood pressure and heart rate)
- Blood sampling for IGF-I and IGFBP-3 determination
- Concomitant medication recording
- Adverse Events recording
- Fundoscopy, if needed
- Drug dispensing, drug accountability and recording

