## **10.4 Analysis of safety endpoints**

### **10.4.1 Carbohydrate metabolism**

Fasting plasma glucose and insulin levels will be measured at baseline, at 6 and 12 months, then annually during GH treatment, and at the end of treatment. For each of these visits descriptive statistics will be calculated and presented together with the absolute and relative changes as compared to baseline.

Insulin resistance will be estimated using both the homeostasis model assessment (HOMA) (Matthews et al 1985) and quantitative insulin sensitivity check index (QUICKI) (Katz et al 2000, WHO 2002). The effect of Omnitrope® treatment on HOMA and QUICKI scores, calculated subsequent to each plasma glucose and insulin measurement, will be evaluated at each visit using descriptive statistics for the observed values along with the changes from baseline.

Glycosylated haemoglobin (HbA1C) will be measured at baseline, at 6 and 12 months and then annually during GH treatment, and at the end of treatment. The effect of treatment on the HbA1C levels will also be displayed using descriptive statistics.

An oral glucose tolerance test (OGTT) will be performed at baseline, at 6 and 12 months and then annually during GH treatment, and at the end of treatment.

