#### Alignment of final visits

A final visit should be performed for all patients terminating study drug. These visits will be analyzed together with the regularly performed study visits. A final visit will be assigned to the appropriate study visit as follows:

In a first step the respective limit between two visit used for assignment, will be assessed as follows: limit = (Day on which VX [= Visit X] should have been performed - Day on which VX-1 should have been performed)/2. The respective limit was rounded if necessary. Days on which a visit should have been performed according to protocol will be assessed as follows (excluding V0 and V1): Month given in the protocol \*(365.25/12) (i.e. V2 = Day 92, V3 = Day 183, V4 = 274 ...).

In a second step final visits performed between VX-1 and the limit (included) will be assigned to VX-1, final visits performed after the limit and prior to VX will be assigned to VX.

For example: A final visit performed between V3 and V4, will be assigned to V3, if performed at or before Day 229 (= (Day 274 + Day 183)/2 = 228.5 => rounded to 229). If performed after Day 229 and at or before V4, the final visit will be assigned to V4.

If due to the assignment of final visits to regular visits two assessments are available for one visit, the assessment nearest to the day on which the visit had to be performed will be used.

If the final visit was performed on the same day as a regular visit, the regular visit will be used for analysis.

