#### **4.6.3 Immunogenicity**

All patients with a positive ADA result at any time during the study will be listed individually.

Tests for anti-rhGH antibodies were performed at baseline, at 3, 6, 9, 12 18 and 24 months, then annually during Omnitrope treatment and the end of treatment. As per protocol amendment 3, the anti HCP testing should be stopped after the amendment became effective in the respective country. Therefore, all HCP results since V01 will be presented up to the Visits occurred until the amendment 3 became effective. Number and percentage of patients with positive test for anti-hGH antibodies and anti-HCP antibodies will be provided by visit and overall (for anti-HCP antibodies).

In addition summary tables and figures for H SDS and HV SDS will be presented for patients with and without positive anti-rhGH antibody test.

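### SAP 4.1 assigns final visits to the nearest visit on the height grid whether or not the test is scheduled there, so end-of-treatment glycaemic, safety-laboratory and anti-hGH results can fall in rows where continuing children have none

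*SAP*

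**What the plan says.** SAP 4.1 (Alignment of final visits) says of final visits: "These visits will be analyzed together with the regularly performed study visits". Each goes to the earlier or later neighbouring visit according to a cut-off day: "final visits performed after the limit and prior to VX will be assigned to VX". If a child then has two assessments for one visit, "the assessment nearest to the day on which the visit had to be performed will be used". Nothing in the rule asks whether the receiving visit schedules the test in question. The footnote to SAP Table 14.1-2 confirms that patients are counted at a visit when their final visit was assigned to it.

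The Protocol Flow Chart places fasting glucose, insulin, HbA1c, OGTT, haematology, chemistry and urinalysis at V01, V03, V05, V09, V11, V13 and later annual visits. Anti-hGH is drawn at V01 to V05, V07, V09, V11, V13 and so on. At V10, V12, V14 the only blood test in Protocol 7.1.11 is "Blood sampling for IGF-I and IGFBP-3 determination". The final visit (Protocol 7.1.12) includes all of these tests.

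Protocol 10.4.1 names end of treatment among the glycaemic time points and continues: "For each of these visits descriptive statistics will be calculated and presented together with the absolute and relative changes as compared to baseline". Protocol 10.4.2 asks for antibody percentages at each time point, end of treatment included. SAP 4.6.3 repeats that antibody schedule ("then annually during Omnitrope treatment and the end of treatment").

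**The concern.** The rule suits height, which is measured at every visit. For tests done at only some visits, it sends part of the end-of-treatment results to visits where nobody continuing is tested. There are two possible outcomes, and the SAP does not choose between them:

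- **The row is printed.** It then looks like a regular visit but describes almost only children who stopped. A change from V09 to V10 to V11 would reflect who is in each row, not time on drug.
- **The row is not printed.** Those end-of-treatment values then drop out of the by-visit tables.

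Either way the annual rows lose those results, and the end-of-treatment summary listed in the Protocol is not delivered. The glycaemic shift shell (Tables 14.3-2.7) and the anti-hGH shell (Table 14.3-3.10) show no end-of-treatment row, and SAP section 3 declares no such change.

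The outputs affected are by-visit means, changes from baseline, HOMA and QUICKI, shift tables and anti-hGH percentages. Anti-hGH is the most exposed: SAP 4.6.3 limits the overall figure to anti-HCP, whose table alone has a total row that includes final assessments.

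**Working it through.** **Reproducing the plan's own figure.** Planned day = month × 365.25/12, which gives 182.6 for V3 and 273.9 for V4, stated as Days 183 and 274. The worked example puts the cut-off at the midpoint: "if performed at or before Day 229 (= (Day 274 + Day 183)/2 = 228.5 => rounded to 229". This reproduces, since (274 + 183)/2 = 228.5, rounded to 229. The general formula is printed differently: "limit = (Day on which VX [= Visit X] should have been performed - Day on which VX-1 should have been performed)/2". That gives (274 − 183)/2 = 45.5, which is half the gap and not a day. It reaches the example only when added to the earlier visit's day (183 + 45.5 = 228.5). The midpoint is used below, and the formula needs correcting in any case.

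**Inputs.** Visits are at months 0, 3, 6, 9, 12, 15, 18, 21, 24, then every 6 months (Flow Chart). Test schedules are as above. Stopping times are not given in the documents, so they are first assumed to be spread evenly.

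**Share of final visits assigned to a visit without the scheduled test.**

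| Stopping period | Glycaemia, safety laboratory | Anti-hGH |
|---|---|---|
| Months 0-12 | V02 (1.5-4.5) + V04 (7.5-10.5): 6/12 = 50% | none: 0% |
| Months 12-24 | V06 to V08 (13.5-22.5): 9/12 = 75% | V06 + V08: 6/12 = 50% |
| Each 12 months after 24 | V10 (27-33) and its successors: 6/12 = 50% | same: 50% |

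A day-by-day count with rounded limits agrees: 50.0%, 75.1% and 49.9% for glycaemia; 0%, 50.1% and 49.9% for antibodies. Over months 0-144 it gives 52.0% and 45.8%.

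**Sensitivity to the stopping pattern.**

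- Equal weight on each of the 28 post-baseline visits to month 144: 15/28 = 53.6% for glycaemia, 12/28 = 42.9% for antibodies.
- A fraction f stopping at V05, the rest evenly over months 12-144: (1 − f) × 52.2% for glycaemia and (1 − f) × 50.0% for antibodies. For f = 10%, 20%, 30%, 50% this is 47%, 42%, 37%, 26% and 45%, 40%, 35%, 25%.
- 75% or 90% of stops at annual laboratory visits, with the remainder all off-schedule: 25% or 10%.

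**What remapping alone would do.** Suppose final values went to the nearest visit at which the test is scheduled, with the collision rule kept. A child stopping at month 29 would go to V09, where that child's own month-24 result is nearer and wins. Assuming even stopping and earlier visits attended, the share of final values lost to collision is:

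- After month 24: now months 24-27, 3/12 = 25%; remapped, months 24-30, 6/12 = 50%.
- Glycaemia, months 12-24: now months 12-13.5, 1.5/12 = 12.5%; remapped, months 12-18, 6/12 = 50%.

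Remapping clears the off-schedule rows but discards more final values.

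**The case against.** The strongest reply is that the key results are untouched. SAP 4.6.2.2 and Tables 14.3-3.7 to 14.3-3.9 count diabetes, IGT and IFG per patient over any visit, so row assignment cannot change them. Every antibody-positive patient is listed individually, the glycaemic parameters have listings, and the study is descriptive with no formal sample size. All of this stands. A reader might infer that the primary diabetes result is distorted; the documents do not support that.

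Three other tempting readings also go too far:

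- **That half of the results are misplaced.** That figure depends on even stopping. The first-year height velocity rule could concentrate final visits at V05, a full laboratory visit, and antibodies are unaffected in year 1.
- **That the rows contain only children who stopped.** Protocol 7.4.6.1 allows extra safety laboratory tests when clinically indicated, so the accurate statement is almost only.
- **That a V10 glycaemic or antibody row will be printed.** The anti-hGH shell skips V06 and the glycaemic shift shell skips V02 and V04, and both then end in an ellipsis. A printed V10 row is an inference. If one were printed, the anti-hGH shell's N column would reveal a small denominator.

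Nearest-time assignment is also defensible in itself: month 31 is one month from V10 and five from V11. That argues against remapping alone. It does not answer the missing end-of-treatment row or the SAP's silence on off-schedule results.

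**Conclusion.** The point holds for the by-visit tables. One rule built on the height grid is applied to tests with sparser schedules, and the SAP does not say how the resulting off-schedule values are shown. Under even stopping, about 50%, 75% and 50% of final glycaemic results are affected in months 0-12, 12-24 and after 24, and 0%, 50% and 50% of anti-hGH results. With clustering at V05 or at annual visits the glycaemic share falls to roughly 10-47%. These shares rest on assumed stopping patterns and on the midpoint cut-off of the worked example.

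The change should be made, but it does not bear on the per-patient diabetes, IGT or IFG counts.

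**What to change.** 1. For fasting glucose, insulin, HbA1c, OGTT, HOMA/QUICKI, anti-hGH and safety laboratory, add a separate end-of-treatment row to the by-visit, change-from-baseline, shift and antibody tables. It should hold the last on-treatment value, with N and time on drug. Protocol 10.4.1 and 10.4.2 already list this time point.
2. State that off-schedule visits are not printed as regular rows for these parameters.
3. If final values are also aligned to visit rows, align them per parameter to that parameter's Flow Chart visits, and state that values displaced by the collision rule still appear in the end-of-treatment row.
4. Keep the present grid for height, weight and vital signs.
5. Correct the printed limit formula so that it matches the worked example.

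The cost is a short edit to SAP 4.1, a parameter-level lookup in the programs and one more row per table. Under item 3, an aligned value may lie up to 6 months from its nominal time.

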#### Retest of fasting blood glucose

Retest values for fasting blood glucose will be listed only.

### 4.2 Disposition of patients and protocol deviations

Information regarding patient enrolment and patient disposition over time will be summarized in a table, listing the participating sites and providing the following variables: site code, number of patients enrolled at screening and number of patients at subsequent visits. Further, a table providing number of patients screened, and number and percentage in each analysis set will be provided.

Protocol deviations were collected based on the PD specification and were classified during the DDRM by the responsible team members. Based on these a summary table and listing of all important protocol deviations will be provided, sorted by site code and patient number. In

addition to site code and patient number, this listing includes: a description of the deviation, the deviation code, and a variable indicating whether the patient discontinued study treatment prematurely. If a patient was withdrawn from the study, date and reason for withdrawal are given.

A listing of all patients who discontinued the study will be provided, sorted by site code and patient number. In addition to site code and patient number, this listing includes date and primary reason for study discontinuation as well as information on last study drug intake. Additionally, number and percentage of patients having completed the study as planned, discontinuing the study prematurely as well as the primary reason for discontinuation will be summarized.

## **4.3 Demographics and baseline characteristics**

### **4.3.1 Demographics**

Demographic data of patients are collected at the screening visit (month 0).

Demographic information will be summarized for age, height, height SDS, height velocity (HV), HV SDS, weight, BMI, BMI SDS, sex, and ethnic origin. Separate summaries of age, sex and ethnic origin will be produced, stratified by initial treatment (powder/solution). Further ethnic origin will be stratified by sex.

Separate tables by country and by age group will be prepared for FAS.

#### **Parents' height**

Parents' height data will be stratified by sex and initial treatment.

#### **Patient birth history**

Birth weight, birth length, birth weight SDS, birth length SDS and gestational age will be summarized for the whole group of patients and stratified by sex and initial treatment. Assessment of birth weight and length SDS is described in the Project Specific Procedure – Calculation of Auxological data v3.0 dated 4-July-2011.

### **4.3.2 Medical history**

Medical history will be recorded at the screening visit and will be coded according to Novartis MedDRA, Version 24.1 or later.

Medical history data will be summarized, providing the proportions resolved, intermittent, and ongoing illnesses by MedDRA system organ class and preferred term for the FAS. Further, all data on medical histories will be listed sorted by site code, patient number, and date of diagnosis.

### **4.3.3 Baseline values of height measurements**

Values for height parameters measured/derived at start of treatment will be summarized for all patients. The summary table will display descriptive statistics for the body height, height SDS, midparental adjusted height SDS, HV, HV SDS and for the time period (in days) between date of visit and historical height measurement used to calculate height velocity at start of treatment.

Midparental adjusted height SDS is defined as H SDS of the patient minus midparental height SDS. The midparental H SDS is defined as  $0.5 * (H \text{ SDS of the mother} + H \text{ SDS of the father})$ .

#### **4.3.4 Pubertal status**

Pubertal status is determined at each visit.

Pubertal status will be summarized for the whole group of patients as well as for the two sexes separately. In these tables, numbers and proportions of Tanner stages will be reported by visit. The tables will be produced for the FAS.

#### **4.3.5 Prior and concomitant medication**

Concomitant medication is documented at each visit from start of treatment onwards.

Medication will be coded to the preferred term using the Novartis WHO drug dictionary version Novartis WHO DDE 17.3-28.08.2018; all possible ATC codes will also be applied.

Prior medication is defined as all medication stopped prior to first intake of study medication. All other medication is considered as concomitant medication.

If stop date of medication is given partial only, the last day of months or 31 December will be assumed. If neither a stop date is given nor ongoing was ticked, the respective medication was regarded as concomitant medication.

Prior and concomitant medication data will be summarized separately by Anatomical Therapeutic Chemical (ATC) term (level 2) and preferred term, providing the proportion of patients to whom medication was administered. This summary will be prepared for the FAS.

### **4.4 Treatment regimen, compliance and exposure to drug**

The patient's exposure to study drug will be calculated from the date of first dose to the date of last study drug administration for patients that prematurely discontinued or completed the study, and presented in years as a decimal.

If date of last study drug administration is missing completely or only a year is given and the patient has discontinued or completed the study, then the date the patient discontinued or completed the study shall be used instead. If date of last study drug administration was given only partial (i.e. month and year given), the first date of the month will be assumed as last administration date. Study drug exposure in days will be converted to study drug in years as follows:

- Exposure (years) = Exposure (days)/365.25.

The patient's exposure to study drug will also be summarized by site for FAS.

The total daily dose administered per kg body weight will be summarized by visit to assess the appropriateness of the applied dose for FAS.

A summary table providing the number and percentage of patients with any study drug dose change documented by reason for dose change overall and by number of times the respective reason was documented per patient will be provided. As for some patients dose change records

were documented when the patient returned to the recommended dose, all records with a daily dose of 0.035 mg/kg will be excluded from the summary tables.

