### **6.5 Treating the patient**

#### **6.5.1 Dose**

A daily dose of 0.035 mg/kg per day will be administered by subcutaneous injection in the evening. A table is provided in the appendix for calculation of the individual dose according to the individual body weight.

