## **7.2 Treatment exposure and compliance**

Patient compliance will be assessed by the collection of used, partly used and unused vials as well as cartridges at each visit. The number of returned vials and the quantity of unused treatment remaining in the vials will provide information on treatment compliance, which will be recorded in the source document at each visit. Patients must comply with the dose schedule. The daily dose should be maintained in the range between 80% and 120% of the recommended daily dose of 0.035 mg/kg BW depending on the patient's responsiveness.

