### **10.3.3 Treatment compliance**

The percentage of medication used compared to the amount prescribed will be analyzed for each visit and the frequency of non-compliant patients (daily dose range <80% or >120%) will be tabulated.

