## 3 Changes to planned analyses

The assessment of laboratory findings related to diabetes mellitus is no longer based on WHO definition of 2006, but on the version published in 2016.

The protocol planned to analyze treatment compliance based on the percentage of medication used compared to the amount prescribed for each visit and the frequency of non-compliant patients (daily dose range 80% or >120%). This approach was changed currently the number of non-compliant patients will be assessed based on the investigator's assessment that is collected on dose change page in the CRF.

Analysis for anti-HCP was added.

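### The filter on dose-change records selects on the dose value (0.035 mg/kg) and not on the reason, so it can remove genuine non-compliance and interruption records from the only table that counts them

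*SAP*

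**What the plan says.** Protocol 7.2 bases compliance on returned drug: "Patient compliance will be assessed by the collection of used, partly used and unused vials as well as cartridges at each visit". Protocol 10.3.3 turns this into two analyses. First, "The percentage of medication used compared to the amount prescribed will be analyzed for each visit". Second, "the frequency of non-compliant patients (daily dose range <80% or >120%) will be tabulated".

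SAP section 3 openly replaces both. In the final analysis "the number of non-compliant patients will be assessed based on the investigator's assessment that is collected on dose change page in the CRF".

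SAP 4.4 has compliance in its title, but the only output it describes that bears on compliance is a summary of dose changes by reason. The shell is Table 14.1-6, which counts patients. Its rows include 'Non-compliance', 'Dose interruption', intolerance of the dosing scheme, a high IGF-1/IGFBP-3 ratio and 'Other', each split by how often the reason was documented.

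The same section adds a filter. Because for some patients dose-change records "were documented when the patient returned to the recommended dose", it says that "all records with a daily dose of 0.035 mg/kg will be excluded from the summary tables".

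That dose is the protocol dose for every child. Protocol 6.5.1 reads: "A daily dose of 0.035 mg/kg per day will be administered by subcutaneous injection in the evening".

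**The concern.** The filter's rationale is about one kind of record, the return to the recommended dose. Its criterion is a dose value, and that value is the dose every child is meant to receive. Nothing in SAP 4.4 limits the exclusion to records whose reason is a return. A record made because a child was non-compliant, or because dosing was interrupted, is deleted too if its dose field reads 0.035 mg/kg.

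Since the compliance analysis now rests on this page, the filter acts on the one table in which non-compliance is counted. The study looks for diabetes during treatment and has no comparator, so a reader of the report will want to know how well the children took the drug. A non-compliance row that is low because of a filtering rule would give false reassurance on that question.

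**Working it through.** The documents state no compliance figure, so there is nothing to reproduce. The check is whether the stated rule matches its purpose, followed by two calculations.

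**Step 1. The passages side by side**

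| Element | Where | Content |
|---|---|---|
| Source of the non-compliance count | SAP 3 | Investigator's assessment on the dose-change page |
| Table that shows it | SAP Table 14.1-6 | 'Non-compliance' row, counted by patient |
| Purpose of the filter | SAP 4.4 | Remove return-to-recommended-dose records |
| Criterion of the filter | SAP 4.4 | Daily dose equal to 0.035 mg/kg, any reason |
| Protocol dose | Protocol 6.5.1 | 0.035 mg/kg per day |

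The criterion covers more than the purpose. Because the table counts patients, one lost record does not remove a patient from a row. A patient disappears from the 'Non-compliance' row only if every 'Non-compliance' record for that patient carries 0.035 mg/kg. The same holds for the 'Dose interruption' row.

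**Step 2. What the dose field might hold**

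SAP 4.4 does not define the field, so I took the dose table in the protocol appendix (5 mg/1.5 ml cartridge) and computed dose dialed ÷ weight for 12.0 to 44.9 kg in 0.1 kg steps, which gives 330 weights.

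- Exactly 0.035: 3 of 330 = 0.9%, namely 0.70/20.0, 1.05/30.0 and 1.40/40.0.
- Equal to 0.035 at three decimals: 185 of 330 = 56%.
- Range: 0.40/12.1 = 0.0331 to 0.45/12.2 = 0.0369 mg/kg.

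If the field holds the nominal prescribed dose, the filter removes every record at the recommended dose, whatever its reason. If it holds a calculated dose per kg, removal depends on the child's weight and on rounding, and many of the return records that the filter is aimed at would survive. If it holds the dose actually taken, a non-compliance or interruption record would usually show a lower value and would survive. The percentages are shares of weight steps. They say nothing about how many non-compliance records are lost.

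**Step 3. Illustration of the effect on the row**

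Reported rate = true rate × (1 − s), where s is the share of non-compliant patients whose only such records are at 0.035 mg/kg. Both the true rate and s are assumptions. N = 278 treated patients (SAP 4.8).

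| Assumed true rate (patients of 278) | s = 0 | s = 25% | s = 50% | s = 100% |
|---|---|---|---|---|
| 10% (28) | 10% | 7.5% | 5.0% | 0% |
| 20% (56) | 20% | 15.0% | 10.0% | 0% |
| 30% (83) | 30% | 22.5% | 15.0% | 0% |

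The documents do not say where s lies. The value s = 0 is possible, and then the row is correct as planned.

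**Step 4. What the filter does not reach**

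SAP 4.4 computes exposure from the date of first dose to the date of last administration, without the dose-change records. Adverse event rates use those years as denominator (SAP 4.6.2.1). The diabetes count comes from laboratory values (SAP 4.5 and Table 14.3-3.7). None of these uses Table 14.1-6.

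**The case against.** The strongest reply is that the affected set may be empty. The CRF page is not in the documents. It records dose changes, so a non-compliance entry may well hold the reduced dose, and an interruption zero. The filter also has a reason drawn from the data: return records exist and would inflate the table. This stands, and it is why the point is conditional.

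Two further replies also stand. The exclusion applies to the summary tables only, so the records remain in Listing 16.2.4.1, which sits under the compliance heading, and some cases may appear as 'Trial treatment deviation' in Table 14.1-16. Neither of these is a count of non-compliant patients. And a child who misses injections with no dose-change record is uncounted with or without the filter. That follows from the change of source disclosed in SAP section 3.

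A reader might infer that the filter overstates exposure and so weakens the denominator behind the diabetes and adverse event results. The documents do not support this, because exposure is computed from dates alone.

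A reader might also want to count children outside the protocol's 80–120% band, that is 0.8 × 0.035 = 0.028 to 1.2 × 0.035 = 0.042 mg/kg, from recorded dose and weight. That would not find missed injections: doses from the table lie between 0.0331 and 0.0369 mg/kg over the weights checked, so a child prescribed the table dose who skips injections stays inside the band. It could also flag dose reductions that Protocol 6.5.4.1 provides for.

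What the replies leave untouched is that the rule as written is broader than its stated purpose.

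**Conclusion.** The point holds as a defect of specification in a descriptive table. As written, SAP 4.4 can remove genuine 'Non-compliance' and 'Dose interruption' records, and Table 14.1-6 is the only table with a row for non-compliance. A patient is lost from a row only if all of that patient's records with that reason are at 0.035 mg/kg.

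The size cannot be derived. It ranges from no effect to an empty row, depending on a CRF field that the documents do not show. Any bias goes one way, towards too few patients in these rows. Confidence that the rule is too broad is high. Confidence that it changes the table is limited. The consequence is minor: no exposure figure, event rate or diabetes count moves, and the individual records remain listed.

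**What to change.** Replace the filter sentence in SAP 4.4 with a rule that does four things:

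- It names the dose field used: nominal prescribed, calculated per kg with the rounding stated, or dose taken.
- It excludes a record at 0.035 mg/kg only when it follows a record at another dose and documents the return to the recommended dose.
- It keeps all other 'Non-compliance' and 'Dose interruption' records whatever their dose.
- It counts a return record that repeats the earlier reason as part of the same episode. Otherwise the rows for how often a reason was documented would count one episode twice.

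The shell of Table 14.1-6 shows no reason code for a return, so returns may have to be identified from the order of a patient's records and the free text under 'Other'. A footnote with the number of records excluded would let the reader see what the rule did.

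No new data are needed. The cost is one SAP sentence, a changed filter and limited manual review of ambiguous records. The change concerns counting only and implies nothing about dosing.
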